4.7 Correlation and [REDACTED]

An exploratory analysis may be done with correlations between pharmacokinetics and/or efficacy endpoints (weight loss, change in hyperphagia scores) and between different instruments will be explored.

4.8 Safety Analyses

4.8.1 Adverse Events (AEs)

Adverse events are to be recorded from signing the informed consent through the Final Study Visit (~ 2 weeks post treatment). All AEs (serious and non-serious) spontaneously reported by the patient and/or in response to an open question from study personnel or revealed by observation, physical examination or other diagnostic procedures will be recorded. An adverse event is considered to be treatment-emergent if the onset date/time is during or after administration of double-blind study drug or, in the event that onset time precedes double-blind study drug administration, the adverse event increases in severity during or after administration of double-blind study drug; in either case through 1-week after the last treatment dose.

Imputations will be used for determining treatment emergence for adverse events with partial dates (see Section 4.2.2); the unimputed partial dates will be included in the data listings.

A top line summary of AE incidence will be presented by treatment group. The number and percentage of patients with any treatment-emergent AE (TEAE), with any TEAE leading to study drug discontinuation, serious TEAE, and with any AE based on an injection site assessment will be summarized by dose group and period. In addition, the TEAE and SAE tables will be analysed by AE severity.

The following AE summaries will be produced by SOC and preferred term, by period:

- Incidence of TEAEs
- Incidence of TEAEs by severity
- Incidence of SAEs
- Incidence of SAEs by severity

A frequency of injection site reactions (Erythema, Edema, Induration, Itching, Pain or Tenderness, Other) will also be produced by each period, summarized by dose group.

All AEs will be provided in a by-patient listing which will include both the term reported on the CRF (verbatim term) and the preferred term and SOC to which it is coded. Relative start and stop days will be included along with the actual onset and resolution dates and times. AEs that are not considered treatment-emergent will be provided in a separate listing.

In addition, separate listings will be provided for the following, whether or not considered to be treatment-emergent (non treatment-emergent AEs will be flagged):

- Serious adverse events (SAEs)
- Adverse events leading to death or discontinuation of study drug (treatment-emergent)
- Adverse events of potential special interest: hypertension, tachycardia, penile erections, changes in female sexual arousal, skin and lesion pigmentation changes (tanning), thromboembolic events. All AEs will be designated AEs of special interest (yes/no and assigned to a category) by blinded review of the study team prior to locking the data base and any unblinding.

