4.5. Withdrawal of Patients

Patients will be informed that they have the right to withdraw from the study at any time for any reason, without prejudice to their medical care. The Investigator also has the right to withdraw patients from the study for any of the following reasons:

Adverse events which justify treatment or study withdrawal. For specific predefined events, additional monitoring and guidance for the Investigator is provided in [Appendices 11.6](#) and [11.7](#).

Non-adherence to study drug regimen or protocol requirements.

Non-compliance with instructions or failure to return for follow-up.

If a patient is withdrawn or discontinued from the study, the primary reason for withdrawal from the study is to be recorded in the source documents/CRF.

All patients withdrawn prior to completing the treatment period should complete the remaining study procedures and visits as outlined for the Early Termination Visit procedures in the Schedule of Assessments in [Section 6](#).

All adverse events must be followed until the post-study follow-up visit, but any skin adverse experiences should continue to be followed, if at all feasible, for ~60-90 days to confirm near, or complete resolution (as has been shown in previous studies).

Approved

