6. STUDY ASSESSMENTS

6.1. Overview of Schedule of Events

The Schedules of Assessments (SOA) to be conducted during the study are depicted in [Table 6-1](#).

After an initial screening and confirmation of eligibility, volunteers will enter a two-week single-blind placebo run-in period (period 1). Those who are compliant in study drug administration and have demonstrated willingness to complete study procedures (weighing, questionnaire and dairy completion), will be randomized to receive subcutaneous doses of RM-493 or placebo for 4 weeks of double-blind treatment (primary efficacy timepoint) (period 2), followed by a 2-week double-blind randomized withdrawal period (period 3). Then patients who complete will be eligible for an optional open label extension treatment for 2 weeks (period 4). Overall, including the run-in, the duration of study drug administration may be up to 10-weeks.

Evaluations will occur at the following times indicated as Study Day numbers: Baseline (one visit between Day -30 and Day -1 in the screening period), ~ the onset of single blind treatment (Day 1), at the end of the single-blind placebo/onset of double blind treatment randomization (Day 15), after 2 weeks of randomized treatment (Day 28), primary evaluations at the end of double-blind study treatment (Day 42), secondary evaluations at the end of the randomized withdrawal period (Day 56), and at the end of the optional open label active drug extension (Day 70).

At the visits, the subjects will undergo safety and efficacy assessments (which may include, but are not limited to, weight, vitals, 12-lead ECG, DEXA, [REDACTED] physical exam, food and behavior questionnaires/diaries) and blood sampling for safety, [REDACTED] and pharmacokinetic evaluations. Evaluations at Day 28 may be conducted via phone, or in-clinic per the SOA.

Participants will not be counseled on food intake or exercise, but will demonstrate an approximately stable diet at randomization by showing stable weight at home for the past two months ($\pm 5\%$).

All subjects also will be followed for approximately 1-3 months after last dose and undergo study termination procedures at the post-study follow up visit (Days 90-163), which may be at next scheduled routine clinic visit if within this timeframe.

Detailed descriptions of the safety, [REDACTED] and pharmacokinetic procedures to be conducted during this study are provided in the following sections.

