Study Period	Screening ⁴	Onset Single-Blind Treatment Run-in ⁴	Double Blind Treatment		End Double Blind/Onset Withdrawal Period	End Withdrawal / Onset Optional Open Label Extension Days 56-69	End Open Label Extension	Post-Study Follow Up
Study Day	Days -30 to -1	Days 1-14	Days 15-41		Days 42-55			Days 90 to 163 ²⁴
Procedure		Run-In ⁴	Onset Treatment Period Day 15±2-	Treatment Period Interim Visit ~Day 28 ^{4,6}	Treatment Period End, Onset Withdrawal Day 42±2	Onset Optional Expansion ~Day 56±2	Final Visit Day 70 -2 or +4	Follow up Visit
Informed consent	X							
Inclusion/Exclusion review	X	X ⁵						
Medical history review	X	X ⁵	X ¹⁵					
Pregnancy test	X	X ⁵	X ^{15, 26}		X	X		X
Physical examination ¹	X		X ¹⁵		X			X
Height	X							
Comprehensive skin exam ²	X							X
Fitzpatrick scale ⁷								
Weight	X	X ⁵	X ¹⁵	X ²³	X	X	X	X
DEXA			X ²²		X ²²			X
Archive sample for storage ¹¹		X ⁵			X			X
Single-Blind placebo practice		X						
Randomization to treatment ³			X ³					
Study treatment administration ¹²		X	X ⁶	X ^{6,23}	X ⁶	X	X	
Injection site inspection ¹³		X	X	X ²³	X	X	X	X
Vital signs ¹⁴	X	X ⁵	X ¹⁵	X ²³	X	X	X	X
ECG (12-lead) ¹⁶	X				X ¹⁶			X
Safety laboratory tests ¹⁷	X		X ¹⁵	X ²³	X		X	X
Questionnaires/Assessments ²⁰	X	X ⁵	X ¹⁵	X	X	X	X	X
PK blood sampling ¹⁸		X ⁵			X ¹⁸	X ²⁵	X ¹⁸	
Basal Metabolic Rate ²¹		X ²¹			X ²¹		X	
Anti-RM-493 antibody samples		X ⁵				X		X
Adverse Event assessment ¹⁹	X	X ⁵	X ¹⁵	X	X	X	X	X
Concomitant meds review	X	X ⁵	X ¹⁵	X	X	X	X	X
Telephone contact ⁸		X		X	X	X		X

Table 6-1: Schedule of Assessments (continued)

- 1 A complete physical examination will be conducted at Screening (or at the discretion of the site, at Day -1), and Day 90. Height will be measured during the Screening Period only.
- 2 A comprehensive skin evaluation will be performed by a dermatologist. Any concerning lesions identified during the screening period will be biopsied and results known to be benign prior to randomization. If the pre-treatment biopsy results are of concern, the patient will be excluded from the study.
- 3 Randomization to occur after all pre-dose procedures completed on Day 15.

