10 Weight is to be measured using the same scale after patients have emptied their bladder and while fasting. Patients are to wear scrubs or equivalent, no shoes, and will be weighed at approximately the same time of day. Weight measurements are to be done in triplicate, [REDACTED]

11 Extra retain samples (2 red top and 2 purple top vacutainer) will be taken pre-dose prior to double-blind study drug, and at the end of the 4-week double blind treatment period before first dose of the withdrawal period.

12 Study drug is administered by patients/caretakers beginning the morning of Day 1 through to Day 70 (-2 days, +4 Days); e.g., the last day of Optional Extension). Patients/caretakers, including home health practitioners, will draw up and self-administer/administer the drug on a daily basis. Home health practitioners may draw up study drug into syringes for storage in refrigerator for up to 2-days in advance, if desired, for patient/caretaker self-administration. On days with clinic visits, the patients/caretaker will administer the drug at the clinic in the presence of the clinical staff. Patients/caretakers will return all empty syringes and vials to the clinic when they visit (the number recorded) and both clinic administered study drug, as well as outpatient study drug administration will be recorded by the patient in a study diary.

13 Injection site evaluations and scoring (by the clinical staff) will include identification and measurement of areas of erythema, edema and induration, as well as the presence of localized pain, tenderness and itching. Additional evaluation data can be collected at any visit where there are injection site reactions even if not a timepoint for formal assessment.

14 All BP and HR measurements are to be obtained in the sitting position following at least 5 minutes of rest. All measurements will be taken in triplicate, approximately 2 minutes apart. On Day 1 and Day 14, patients will have vitals obtained pre-dose. When possible, BP should be taken in the same arm throughout the study, using the same methodology (automated or manual). Body temperature (°C) and respiration rate (breaths/minute) will be obtained in the sitting position following at least 5 minutes of rest.

15 On Treatment Day 14, at the end of the single-blind placebo run-in but prior to beginning dosing in the 4 week double blind treatment period.

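### The SAP's 1-week treatment-emergent cutoff conflicts with open-ended definitions elsewhere and leaves skin changes dated to the follow-up dermatology exam out of the incidence tables

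*SAP*

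**What the plan says.** **Treatment-emergent definition.** SAP 4.8.1 states: "An adverse event is considered to be treatment-emergent if the onset date/time is during or after administration of double-blind study drug". It also admits earlier events that worsen on or after double-blind drug, and closes both routes with "in either case through 1-week after the last treatment dose". The test is on onset or worsening, not on when the event was detected.

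**Other definitions.** Footnote 19, in both Protocol Table 6-1 and SAP Appendix 1, makes every event reported after randomization treatment-emergent. Protocol section 7 does so for every event after study drug starts. Neither has an end date.

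**Skin exam.** Footnote 2 of the schedule states: "A comprehensive skin evaluation will be performed by a dermatologist". Both schedules mark this exam in two columns only, Screening and Post-Study Follow Up. Protocol 6.1 has all subjects "undergo study termination procedures at the post-study follow up visit (Days 90-163" and gives the same visit as roughly 1-3 months after the last dose.

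**Dosing.** SAP Appendix 1, footnote 12: "Study drug is administered by patients/caretakers beginning the morning of Day 1 through to Day 70 (-2 days, +4 Days". Patients who decline the extension stop at about Day 56 (±2).

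**Outputs.** The incidence tables in SAP 4.8.1 cover TEAEs and SAEs. For the rest, "AEs that are not considered treatment-emergent will be provided in a separate listing". Events of special interest, which include skin and lesion pigmentation changes, are listed whether or not treatment-emergent, with a flag.

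**End of recording.** SAP 4.8.1 records adverse events "through the Final Study Visit (~ 2 weeks post treatment", whereas both schedules mark adverse event assessment at the Days 90-163 visit.

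**The concern.** Safety and tolerability is a primary objective. Protocol 7.3 lists skin darkening among the fairly common effects of the drug and names cancerous change in skin lesions for careful assessment. The comprehensive exam is the scheduled assessment designed to find such changes, yet after treatment it takes place only once the SAP window has closed.

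Other scheduled checks leave part of the gap open. Physical examinations are marked at Screening, Day 15 (before double-blind dosing), Day 42 and follow-up. None is marked at Day 56 or Day 70, and Protocol 6.4.3 describes the skin part of the abbreviated exam as not comprehensive. For changes arising in the withdrawal period or on 2.5 mg open-label drug, the next scheduled skin examination is therefore at follow-up. Injection-site inspections continue but look only at injection sites.

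Two things are at stake: whether the incidence tables show what that exam finds, and whether two programmers reading the same documents would flag the same events.

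**Working it through.** The plan gives no figure of its own to reproduce. The check is day arithmetic followed by a comparison of the rules.

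**1. When the window closes.** Inputs are the last dose day L (Day 70 −2/+4 with the extension, Day 56 ±2 without), the 7-day limit in SAP 4.8.1, and follow-up at Days 90-163. Closing day = L + 7. Gap = exam day − (L + 7).

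| Last dose L | Window closes | Gap to Day 90 | Gap to Day 163 |
|---|---|---|---|
| 68 (extension, earliest) | 75 | 15 | 88 |
| 70 (extension, nominal) | 77 | 13 | 86 |
| 74 (extension, latest) | 81 | 9 | 82 |
| 54 (no extension, earliest) | 61 | 29 | 102 |
| 56 (no extension, nominal) | 63 | 27 | 100 |
| 58 (no extension, latest) | 65 | 25 | 98 |

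The smallest gap is 9 days. If follow-up is timed as 1-3 months after the last dose instead, taken as 30 to 90 days, the gap is 30 − 7 = 23 to 90 − 7 = 83 days. On either timing the exam falls after the window.

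**2. The follow-up timings do not agree.** Day 90 is 90 − 74 = 16 to 90 − 68 = 22 days after the last extension dose, which is less than 1 month. Day 163 is 163 − 56 = 107 days after a Day 56 last dose, which is more than 3 months. The largest gaps in the table therefore use follow-up days beyond the 1-3 month description. The SAP's figure of about 2 weeks after treatment matches neither statement.

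**3. How a change first seen at that exam is classified.**

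| Recorded onset | SAP 4.8.1 with 4.2.2 | Footnote 19 and Protocol section 7 |
|---|---|---|
| Visit date, non-serious | Not treatment-emergent; listings only | Treatment-emergent |
| Visit date, serious | Not treatment-emergent, but the SAE table is not worded as limited to TEAEs | Treatment-emergent |
| Dated back to dosing or the following week | Treatment-emergent | Treatment-emergent |
| Missing, or too incomplete to rule out the window | Treatment-emergent by the worst-case rule | Treatment-emergent; no upper limit applies |

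The first row is the defect: the documents disagree, and the operative SAP rule removes the event from every planned incidence table. The worst-case rule in SAP 4.2.2 does not help there, because a visit date is a complete date. The SAP has no rule for dating a change first detected at an examination, so one onset field decides whether the event counts.

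**The case against.** A reader might infer that nothing first found at the follow-up exam can reach the treatment-emergent tables. The documents do not support that. The rule tests onset, so a change that the patient or caretaker dates to the dosing period counts, and SAP 4.2.2 counts one whose onset date is missing or insufficient. Gradual darkening is a natural candidate for an imprecise date.

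A reader might also infer that cases are lost or that skin goes unexamined on treatment. Neither is so. Every case stays in a listing, and with about 36 patients a rate can be counted by hand. An abbreviated exam including skin falls on Day 42, adverse events are assessed at every visit, and telephone contacts fill longer intervals. Protocol 6.2.2 reports that pigmentation reversed after stopping drug, which makes notice during dosing more likely than first appearance months later. The instruction in Protocol 4.5 that "any skin adverse experiences should continue to be followed, if at all feasible, for ~60-90 days" concerns resolution of known events, not detection of new ones. The dermatological guidance said to be in the appendix is not visible in the public text, so unscheduled dermatology review cannot be excluded.

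Finally, follow-up comes after the withdrawal randomization and, for many, open-label drug. Any table of events dated there is uncontrolled.

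These points stand and limit the concern to events with a complete onset date after the window. They do not remove the conflict between definitions, supply the missing onset rule, or put a visit-dated, non-serious skin event into a planned table.

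**Conclusion.** The point holds for a non-serious skin or pigmentation change first recorded at the follow-up dermatology exam with a complete onset date after the SAP window, typically the visit date. Such an event is treatment-emergent under footnote 19 and Protocol section 7, but SAP 4.8.1 excludes it from the incidence tables. The exam follows window closure by 9 to 102 days over the scheduled visit ranges, or 23 to 83 days if follow-up is timed at 30 to 90 days after the last dose.

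This assumes the planned schedule, the last dose on the visit day, and exam columns as they appear in both schedules. Protocol 6.1 lets visit windows be treated as approximate, but for Day 90 to fall inside the window the last dose would have to be on Day 83 or later (90 − 7 = 83), 9 days past the latest scheduled day. The documents give no frequency for such findings, so the number of events affected cannot be estimated. The change should be made before unblinding because it decides which skin events are counted under a primary safety objective. Efficacy analyses are not affected.

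**What to change.** 1. **Reconcile the definitions.** Align SAP 4.8.1, footnote 19 in both schedules and Protocol section 7 on one treatment-emergent definition, including its start and its end.
2. **Settle the skin events.** For skin and pigmentation events of special interest, count events through the post-study follow-up visit. Alternatively, state how onset is assigned when a change is first detected at that exam. Other events can keep the 1-week limit if the reconciled definition retains it.
3. **Add one table.** Give descriptive incidence of these events through follow-up by last active dose, labelled as an exposure summary and not a randomized comparison.
4. **Correct the timing.** Reconcile the SAP's end of recording at about 2 weeks after treatment with the 1-3 month and Days 90-163 follow-up, and those two with each other.

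The cost is SAP wording, a matching protocol clarification, one derived flag and one table, all from data already collected. The downside is that some late skin findings unrelated to drug will be counted; the existing listings let a reader identify them.

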3. INVESTIGATIONAL PLAN

3.1. Overall Design and Plan of the Study

This will be a randomized, double-blind, placebo-controlled, parallel group study. It will consist of 4 sequential periods:

- (1) a 2-week single-blind, placebo-controlled baseline period with approximately one third receiving a lower volume placebo run-in dose and approximately two-thirds receiving a higher volume placebo-run-in dose;
- (2) a 4-week, double blind, placebo-controlled, randomized parallel group period (primary analysis timepoint) where patients will be randomized 2:1:3 to placebo or one of two dose levels of RM-493; and
- (3) a 2-week, double-blind, randomized withdrawal period where half of each RM-493 group will remain on the same dose of active drug and the other half will receive placebo, and half of the placebo group will receive RM-493 at a corresponding dose/volume level.
- (4) In addition, there will be an optional 2-week open label extension period (period 4) where every patient can participate and receive open label RM-493.

Approximately 36 subjects will be randomized to a placebo arm or one of 2 dosing arms with a 2:1:3 assortment between placebo, lower dose of RM-493 and higher volume RM-493. In the first half of the study, dosing arms were 0.5 mg or 1.5 mg RM-493. Based on the results of the interim analysis, in the second half of the study, dosing arms will be 1.5 RM-493 and 2.5 RM-493. *Subjects will initiate with 2 weeks of single blind placebo lead-in phase, using a 0.5 mg (50 mcL), 1.5 mg (150 mcL), or 2.5 mg (250 mcL) dose volume corresponding to the eventual dose of active drug or placebo they will receive during periods 2 and 3, after which they will be randomized 2:1:3 to receive daily lower volume or higher volume SC doses of placebo, or RM-493 for 4 weeks.*

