Subjects will initiate with 2 weeks of single blind placebo lead-in phase using either a lower or higher dose volume corresponding to the eventual dose of active drug or placebo they will receive during periods 2 and 3, after which they will be randomized 2:1:3 to receive daily SC doses for 4 weeks of placebo, or 0.5 mg or 1.5 mg of RM-493 in the first half of the trial, or placebo, or 1.5 mg or 2.5 mg of RM-493 in the second half of the trial.

After completion of the primary 4-week, double-blind treatment (period 2), a double-blind, randomized placebo withdrawal (period 3) will initiate: patients within each of the RM-493 groups will be randomized 1:1 to either continue with the same dose or begin placebo treatment with the same dose volume, all using the same dose/volume regardless of remaining on active RM-493 or switching to placebo as part of the randomization. The patients in the placebo group during the 4 week primary treatment period would also be randomized 1:1 to continue on placebo or to receive RM-493 at the corresponding dose/volume established during periods 1 and 2 during the randomized withdrawal phase (period 3).

A follow-up open label extension phase of the trial (after the initial 4 weeks of study duration and the 2-weeks of randomized withdrawal) will be available for patients who completed the trial and wish to continue in the 2-week open label extension. For this final treatment period, all subjects will receive 2.5 mg (250 mcL) of RM-493 for 2 weeks.

Since the volume of administration is different for the different doses of RM-493, placebo patients will be allocated to matching placebo at matching volumes to maintain the blinded nature of the study throughout all study periods except for the final open-label active period. All subjects in this final open-label, active treatment phase (period 4) will receive 2.5 mg (250 mcL) of RM-493. The allocation schedule will be so constructed to account for this study design feature. A schema of dose allocation during the study is depicted in [Figure 5.2](#).

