4.2 General Considerations

Data will be described and analyzed using the Statistical Analysis System (SAS), version 9.2 or higher on a Windows platform (SAS Institute Inc., Cary, NC). Adverse events and medical history will be coded using MedDRA Version 18.1. Prior and concomitant medications will be coded to provide Anatomical Therapeutic Chemical (ATC) levels 2 (therapeutic main groups) and 4 (chemical subgroups) using the December 2014 version of the World Health Organization (WHO) Drug Dictionary.

Individual patient data will be presented in by-patient data listings. Descriptive statistics (number of patients [n], mean, standard deviation [SD], median, minimum [Min] and maximum [Max]) will be presented for continuous data. For categorical data, the frequency and percentage of patients in each category will be presented; percentages will be based on the number of patients with non-missing observations.

Unscheduled visits will not be used, unless they meet the criteria for a baseline observation (e.g. last observation prior to initial double-blind drug administration).

A by-patient listing will be provided which includes all derived efficacy data for which the derivation is not otherwise provided. The data as collected will be provided in the relevant by-patient listing of the raw data.

Unless specified otherwise, by-patient listings will be provided for all data as contained in the raw database.

Reporting of treatment groups in summary tables will be performed with placebo groups (high and low dose groups) combined. The primary focus for the treatment group analysis will be on Period 2 (the 4-week double blind period). Additional analyses will focus on specific intervals (Period 3; effect of randomized change in treatment from active to placebo, and placebo to active); Period 4 (the open label, 1.5 mg dose 2-week active extension), and Period 1 (the double-blind, placebo controlled run-in period).

The final study analysis will include summaries from pooled data using identical active doses (e.g., 0.5 mg, 1.5 mg, 2.5 mg) across the whole study, including data from before and after any interim analysis. As mentioned above, all placebo data will be pooled as well.

Supplemental exploratory analyses will be done for Period 1 (run-in) data to help in understanding of the variability of PWS subjects in a clinical trial; this data will complement the placebo data obtained later in the trial.

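### Injection-site reactions at 2.5 mg and 0.5 mg are tabulated against a pooled placebo group that mostly injected a different vehicle volume

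*SAP*

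**What the plan says.** SAP 4.8.1 plans a frequency of injection-site reactions (erythema, edema, induration, itching, pain or tenderness, other) that "will also be produced by each period, summarized by dose group". That section does not say how placebo is shown. The rule is in SAP 4.2: "Reporting of treatment groups in summary tables will be performed with placebo groups (high and low dose groups) combined". The same section pools over both halves of the study, giving summaries from "pooled data using identical active doses (e.g., 0.5 mg, 1.5 mg, 2.5 mg) across the whole study", and adds that "all placebo data will be pooled as well".

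In Protocol 3.1 the run-in volume is set by the later treatment, "using a 0.5 mg (50 mcL), 1.5 mg (150 mcL), or 2.5 mg (250 mcL) dose volume", with "approximately one third receiving a lower volume placebo run-in dose and approximately two-thirds receiving a higher volume placebo-run-in dose". Protocol 5.2 keeps that volume through Periods 2 and 3 and states: "Since the volume of administration is different for the different doses of RM-493, placebo patients will be allocated to matching placebo at matching volumes". Placebo is the vehicle (Protocol 5.1), and the formulation is lipid-based (Protocol 1.3.3.3).

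Protocol 2.2 also says that tolerability will be compared across dose levels and with the placebo lead-in. Neither document plans injection-site reactions by placebo volume or any adjustment for volume.

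**The concern.** In the active arms dose and volume are fully collinear: every 2.5 mg patient injects 250 µL and every 0.5 mg patient 50 µL. Only vehicle given at the same volume can separate a local effect of the drug from a local effect of the injected vehicle. The trial has such patients, but the pooling rule merges them with patients on other volumes.

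Safety and tolerability is a primary objective (Protocol 2.1.1), and injection-site evaluation is a listed safety endpoint (SAP 3.3.4). Only reactions that the investigator judges clinically significant become adverse events (Protocol 6.4.13 and 7.2), so this frequency table is the main summary of local tolerability. SAP section 1 says the study is to inform Phase 3 design. If vehicle volume matters, the table could show a gradient over dose that partly or wholly reflects volume.

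**Working it through.** The plan gives no figure for this table, so the check starts from its allocation.

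**Inputs.** About 20 patients in the first half (0.5 and 1.5 mg) and 16 in the second (1.5 and 2.5 mg), allocated 2:1:3 to placebo, lower and higher dose (SAP 3.1 and 3.2). Volumes are from Protocol 3.1.

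**Expected active groups.**
- 0.5 mg: 20 × 1/6 = 3.3
- 1.5 mg: 20 × 3/6 + 16 × 1/6 = 12.7
- 2.5 mg: 16 × 3/6 = 8.0

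The lower-volume active arms sum to 3.3 + 2.7 = 6 and the higher-volume arms to 10 + 8 = 18, which reproduces the counts in Protocol 3.1.

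**Placebo split.** Placebo is 20 × 2/6 = 6.7 in the first half and 16 × 2/6 = 5.3 in the second, 12 in all. If a fraction f of placebo takes the lower volume, the lower-volume share of all patients is 1/6 + f × 2/6. Setting this to one third, as in Protocol 3.1, gives f = 1/2. This 1:1 split is inferred, not stated.

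**Placebo by volume at 1:1.**
- 50 µL: 6.67 × 0.5 = 3.3 (28%)
- 150 µL: 6.67 × 0.5 + 5.33 × 0.5 = 6.0 (50%)
- 250 µL: 5.33 × 0.5 = 2.7 (22%)
- Mean: (3.33 × 50 + 6 × 150 + 2.67 × 250)/12 = 144 µL

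So 100 − 22 = 78% of the placebo set against 2.5 mg, and 100 − 28 = 72% of that set against 0.5 mg, had another volume. This part needs no assumption about reaction rates.

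**Apparent effect of a locally inert drug.** It equals the risk at the dose's own volume minus the pooled placebo risk. With assumed risks of 10%, 20% and 30%, the pooled risk is (3.33 × 0.10 + 6 × 0.20 + 2.67 × 0.30)/12 = 19.4%. The differences are 10 − 19.4 = −9.4, 20 − 19.4 = +0.6 and 30 − 19.4 = +10.6 points.

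| Assumed vehicle risk at 50/150/250 µL | Pooled placebo | 0.5 mg | 1.5 mg | 2.5 mg |
|---|---|---|---|---|
| 20/20/20% | 20.0% | 0 | 0 | 0 |
| 5/10/15% | 9.7% | −4.7 | +0.3 | +5.3 |
| 10/20/30% | 19.4% | −9.4 | +0.6 | +10.6 |
| 10/30/50% | 28.9% | −18.9 | +1.1 | +21.1 |

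If placebo were split 1:3 instead, the counts would be 1.7, 6.3 and 4.0 with mean 169 µL, and the 10/20/30% row would read −11.9, −1.9 and +8.1.

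**Period 1, when everyone is on vehicle.** Adding active and placebo patients by volume gives 3.3 + 3.3 = 6.7 at 50 µL, 12.7 + 6.0 = 18.7 at 150 µL and 8.0 + 2.7 = 10.7 at 250 µL.

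**Period 3.** Half of 12 placebo patients (6) stay on placebo, and half of 24 active patients (12) move to it. Placebo recipients in that period are therefore one third never treated and two thirds recently withdrawn from RM-493.

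**The case against.** **Much of the comparison is already planned.** The table is by period, so it includes Period 1, and Protocol 2.2 promises a comparison with the lead-in. If Period 1 is shown by later dose group, the active columns give vehicle-only rates in about 3.3, 12.7 and 8.0 patients at the three volumes. By-patient listings are planned too. This stands in part. A before/after comparison is confounded with time and cumulative injections, the placebo column stays pooled in Period 1, and the SAP does not say how the Period 1 columns are formed.

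**Pooling can be the better estimate.** At 10/20/30%, the pooled rate has a standard error of about 11 points. With its bias of 10.6, the root mean squared error as an estimate of the 250 µL rate is about 15 points, against a standard error of about 28 in a matched cell of 2.7 patients. At 50 µL the two are close (about 15 and 16). At 10/30/50%, pooling still wins at 250 µL (about 24 against 31) but loses at 50 µL. This stands as a reason to keep the pooled column. It is no reason to leave the volume-specific counts out of a descriptive table.

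**Three stronger readings are not supported.** A reader might infer that a dose gradient in this table would be merely a volume gradient. The documents contain no data on vehicle volume and local reactions, and the table carries no test and no rule attributing reactions to the drug. A reader might infer that placebo was matched to serve as the tolerability comparator. The stated purpose is blinding: "placebo patients will be allocated to matching placebo at matching volumes to maintain the blinded nature of the study". A reader might also infer that visible volume reveals treatment to caregivers who rate hyperphagia. Neither document says caregivers know the allocation by volume, and that would be a separate efficacy question.

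**Conclusion.** The point holds as a limited one. The volume mismatch follows from the allocation and the pooling rule: about 78% of the comparator for 2.5 mg and 72% of that for 0.5 mg, under the inferred 1:1 placebo split. Bias arises only if vehicle volume affects local reactions. It would then run upward at 2.5 mg and downward at 0.5 mg if risk rises with volume. At 1.5 mg, the largest active group, it is about 1 point or less in the scenarios at the 1:1 split, because 150 µL is close to the pooled mean. This relies on risk being roughly linear in volume. Across the assumed risks the bias runs from zero to about +21 and −19 points. These figures illustrate sensitivity and are not estimates for this product. The point concerns a descriptive table in a pilot study and does not touch the efficacy analyses.

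**What to change.** For the injection-site reaction table only, write into SAP 4.8.1 an exception to the pooling rule of SAP 4.2:

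1. **Period 1:** show reactions by injected volume (50, 150, 250 µL) for all patients, with a within-patient display of Period 1 against Period 2. This is the largest available look at vehicle volume itself.
2. **Period 2:** add descriptive placebo columns by volume, each beside the dose of the same volume, and keep the pooled placebo column.
3. **Period 3:** if shown by volume, separate patients on continuous placebo from those withdrawn from RM-493.

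The cost is a few extra columns from data already collected. The downside is Period 2 placebo cells of about 3 to 6 patients, and smaller ones in Period 3, so the added columns should be labelled descriptive and carry no test.
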